5.5.4.3. Pulmonary irAEs

Rule out non-inflammatory causes. If a non-inflammatory cause is identified, treat accordingly and continue therapy per protocol. Evaluate with imaging and pulmonary consultation.

Table 5-5. Pulmonary irAE Management Algorithm

| Pulmonary irAEs | | |
|---|---|---|
| CTCAE Grade of Pneumonitis | Management | Follow-up |
| Grade 1 Radiographic changes only. | Consider delay of GS-1423 therapy per protocol. Monitor for symptoms every 2-3 days. Consider pulmonary and infectious disease consults. | Re-image every \geq 3 weeks. If worsens: Treat as Grade 2 or Grade 3-4. |
| Grade 2 Mild to moderate new symptoms. | Delay GS-1423 therapy per protocol. Pulmonary and infectious disease consults. Monitor symptoms daily; consider hospitalization. 1 mg/kg/day methylprednisolone IV or oral equivalent. Consider bronchoscopy, lung biopsy. | Re-image every 1-3 days. If improves: When symptoms return to near baseline, taper corticosteroids over \geq 1 month, then resume GS-1423 therapy per protocol, and consider prophylactic antibiotics. If not improving after 2 weeks or worsening: Treat as Grade 3-4. |
| Grade 3-4 Severe new symptoms; new/worsening hypoxia; life-threatening. | Discontinue GS-1423 therapy per protocol. Hospitalize. Pulmonary and infectious disease consults. 2-4 mg/kg/day methylprednisolone IV or IV equivalent. Add prophylactic antibiotics for opportunistic infections. Consider bronchoscopy, lung biopsy. | If improves to baseline: Taper corticosteroids over \geq 6 weeks. If not improving after 48 hours or worsening: Add additional immunosuppression (eg, infliximab, cyclophosphamide, IV immunoglobulin, mycophenolate mofetil). |

CTCAE Common Terminology Criteria for Adverse Events; irAE immune related adverse event; IV intravenous.

5.5.4.4. Hepatic irAEs

Rule out non-inflammatory causes. If a non-inflammatory cause is identified, treat accordingly and continue therapy per protocol. Consider imaging for obstruction.

Table 5-6. Hepatic irAE Management Algorithm

| Hepatic irAEs | | |
|--|--|---|
| CTCAE Grade of Liver Test Elevation | Management | Follow-up |
| Grade 1 AST or ALT > ULN to $3 \times$ ULN or total bilirubin > ULN to $1.5 \times$ ULN. | Continue GS-1423 therapy per protocol. | Continue liver function tests (LFT) monitoring per protocol. If worsens: Treat as Grade 2 or Grade 3-4. |
| Grade 2 AST or ALT > 3 to $\leq 5 \times$ ULN or total bilirubin > 1.5 to $\leq 3 \times$ ULN. | Delay GS-1423 therapy per protocol. Increase frequency of monitoring to every 3 days. If subject has concurrent AST or ALT > $3 \times$ ULN and total bilirubin > $2 \times$ ULN > 7 days, discontinue GS-1423 therapy per protocol. | If returns to baseline: Resume routine monitoring; resume GS-1423 therapy per protocol. If elevations persist > 5 to 7 days or worsen: 0.5-1 mg/kg/day methylprednisolone IV or oral equivalent. When LFT returns to Grade 1 or baseline, taper corticosteroids over ≥ 1 month, consider prophylactic antibiotics for opportunistic infections, and resume GS-1423 therapy per protocol. |
| Grade 3-4 AST or ALT > $5 \times$ ULN and/or total bilirubin > $3 \times$ ULN. | Discontinue GS-1423 therapy per protocol. Increase frequency of monitoring to every 1-2 days. 1-2 mg/kg/day methylprednisolone IV or oral equivalent. ^a Add prophylactic antibiotics for opportunistic infections. Consult gastroenterology. Consider obtaining MRI/CT scan of liver and liver biopsy if clinically warranted. | If returns to Grade 2: Taper corticosteroids over ≥ 1 month. If does not improve in > 3 to 5 days, worsens or rebounds: Add mycophenolate mofetil 1 g twice daily. If no response within an additional 3-5 days, consider other immunosuppressants per local guidelines. |

ALT alanine aminotransferase; AST aspartate aminotransferase; CT computed tomography; CTCAE Common Terminology Criteria for Adverse Events; irAE immune related adverse event; IV intravenous; LFT liver function test; MRI magnetic resonance imaging; ULN upper limit of normal.

a The recommended starting dose for Grade 4 hepatitis is 2 mg/kg/day methylprednisolone IV.

5.5.4.5. Endocrine irAEs

Rule out non-inflammatory causes. If a non-inflammatory cause is identified, treat accordingly and continue therapy per protocol. Consider visual field testing, endocrinology consultation, and imaging.

Table 5-7. Endocrine irAE Management Algorithm

| Endocrine irAEs | | |
|---|---|---|
| Endocrine Disorder | Management | Follow-up |
| Asymptomatic TSH abnormality. | Continue GS-1423 therapy per protocol. If $TSH < 0.5 \times \text{lower limit of normal (LLN)}$ or $TSH > 2 \times \text{ULN}$, or consistently out of range in 2 subsequent measurements: Include free thyroxine at subsequent cycles as clinically indicated; consider endocrinology consult. | |
| Symptomatic endocrinopathy. | Evaluate endocrine function. Consider pituitary scan. Symptomatic with abnormal lab/pituitary scan: Delay GS-1423 therapy per protocol; 1-2 mg/kg/day methylprednisolone IV or oral equivalent; initiate appropriate hormone therapy. No abnormal lab/pituitary MRI scan but symptoms persist: Repeat labs in 1-3 weeks, MRI in 1 month. | If improves (with or without hormone replacement): Taper corticosteroids over ≥ 1 month and consider prophylactic antibiotics for opportunistic infections. Resume GS-1423 therapy per protocol. Subjects with adrenal insufficiency may need to continue corticosteroids with mineralocorticoid component. |
| Suspicion of adrenal crisis (eg, severe dehydration, hypotension, shock out of proportion to current illness) | Delay or discontinue GS-1423 therapy per protocol. Rule out sepsis. Stress dose of IV corticosteroids with mineralocorticoid activity. IV fluids. Consult endocrinologist. If adrenal crisis ruled out, treat as above for symptomatic endocrinopathy. | |

irAE immune related adverse event; IV intravenous; LLN lower limit of normal; MRI magnetic resonance imaging; TSH thyroid stimulating hormone; ULN upper limit of normal.

5.5.4.6. Renal irAEs

Rule out non-inflammatory causes. If a non-inflammatory cause is identified, treat accordingly and continue therapy per protocol.

Table 5-8. Renal irAE Management Algorithm

| Renal irAEs | | |
|---|--|--|
| CTCAE Grade of Creatinine Elevation | Management | Follow-up |
| Grade 1 Creatinine > ULN and > baseline but $\leq 1.5 \times$ baseline. | Continue GS-1423 therapy per protocol. Monitor creatinine weekly. | If returns to baseline: Resume routine creatinine monitoring per protocol. If worsens: Treat as Grade 2 or Grade 3-4. |
| Grade 2-3 Creatinine $> 1.5 \times$ baseline to $\leq 6 \times$ ULN. | Delay GS-1423 therapy per protocol. Monitor creatinine every 2-3 days. 0.5-1.0 mg/kg/day methylprednisolone IV or oral equivalent. Consider renal biopsy. | If returns to Grade 1: Taper corticosteroids over ≥ 1 month, consider prophylactic antibiotics for opportunistic infections, and resume GS-1423 therapy and routine creatinine monitoring per protocol. If elevations persist > 7 days or worsen: Treat as Grade 4. |
| Grade 4 Creatinine $> 6 \times$ ULN | Discontinue GS-1423 therapy per protocol. Monitor creatinine daily. 1.0-2.0 mg/kg/day methylprednisolone IV or oral equivalent. Consult nephrologist. Consider renal biopsy. | If returns to Grade 1: Taper corticosteroids over ≥ 1 month and add prophylactic antibiotics for opportunistic infections. |

CTCAE Common Terminology Criteria for Adverse Events; irAE immune related adverse event; IV intravenous; ULN upper limit of normal.

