Transient (\leq 3 days) Grade 3 fatigue, local reactions, headache, nausea, emesis, or diarrhea that are controlled with medical management and/or resolves to Grade \leq 1
Transient (\leq 3 days) Grade 3 flu-like symptoms or fever, which are controlled with medical management
An event clearly associated with the underlying disease, PD, a concomitant medication, or comorbidity.

Dosing/procedures-related toxicities

- Inability to receive the first 2 doses of GS-1423 because of related toxicity, even if the toxicity does not meet DLT criteria defined above (regardless of dosing schedule)

Note: Exceptions include DLT exclusions mentioned above.

- Greater than a 2-week delay in starting the next cycle of therapy due to a treatment-related toxicity, even if the toxicity does not meet the DLT criteria determined above

Grade 5 event (ie, death)

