5.5.4. Management of Potential Immune-Related Adverse Events

Immune-related AEs may be associated with immuno-oncology agents such as GS-1423 and will be categorized as AEs of interest in this study. An irAE is defined as an AE of unknown etiology, that is potentially associated with study drug exposure and is consistent with an immune-mediated phenomenon. Efforts should be made to rule out other etiologies prior to labeling an AE of clinical interest. Early recognition and management of irAEs may mitigate

severe toxicity. Investigators should also monitor subjects closely for potential irAEs, which may manifest after weeks of treatment, at the earliest. Such events may consist of persistent rash, diarrhea, colitis, autoimmune hepatitis, pneumonitis, encephalitis, arthritis, glomerulonephritis, cardiomyopathy, or uveitis and other inflammatory eye conditions.

Management algorithms have been developed to assist investigators in assessing and managing the following groups of irAEs: dermatological, gastrointestinal, pulmonary, hepatic, endocrine renal, and neurological, among others.

Adverse events (both non-serious and serious) associated with drug exposure and consistent with an immune phenomenon may represent an immunologic etiology. These irAEs may be predicted based on the nature of the study drugs, their mechanism of action, and reported experience with immunotherapies that have a similar mechanism of action. An irAE can occur any time from shortly after the first dose to several months after the last dose of treatment. Particular attention should be paid to AEs that may be suggestive of potential irAEs, as outlined below.

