5.5.4.2. Gastrointestinal irAEs

Rule out non-inflammatory causes. If a non-inflammatory cause is identified, treat accordingly and continue therapy. Opiates/narcotics may mask symptoms of perforation. Infliximab should not be used in cases of perforation or sepsis.

Table 5-4. Gastrointestinal irAE Management Algorithm

| Gastrointestinal irAEs | | |
|--|--|---|
| CTCAE Grade of Diarrhea / Colitis | Management | Follow-up |
| Grade 1 Diarrhea: < 4 stools/day over baseline. Colitis: asymptomatic. | Continue GS-1423 therapy per protocol. Symptomatic treatment. | Close monitoring for worsening symptoms. Educate subject to report worsening immediately. Consider symptomatic treatment including hydration, electrolyte replacement, dietary changes (eg, American Dietetic Association colitis diet), and loperamide. If worsens: Treat as Grade 2 or 3-4. |
| Grade 2 Diarrhea: 4-6 stools per day over baseline; IV fluids indicated < 24 h; not interfering with activities of daily living (ADL). Colitis: abdominal pain; blood in stool. | Delay GS-1423 therapy per protocol. Symptomatic treatment. | If improves to Grade 1: Resume GS-1423 therapy per protocol. If persists > 5 to 7 days or recurs: 0.5-1 mg/kg/day methylprednisolone or equivalent. When symptoms improve to Grade 1, taper corticosteroids over \geq 1 month; consider prophylactic antibiotics for opportunistic infections; resume GS-1423 therapy per protocol. If worsens or persists > 3 to 5 days with oral corticosteroids: Treat as Grade 3-4. |
| Grade 3-4 Diarrhea (Grade 3): \geq 7 stools per day over baseline; incontinence; IV fluids \geq 24 h; interfering with ADL. Colitis (Grade 3): severe abdominal pain, medical intervention indicated, peritoneal signs. Grade 4: life-threatening, perforation | Discontinue GS-1423 therapy per protocol. 1-2 mg/kg/day methylprednisolone IV or equivalent. Add prophylactic antibiotics for opportunistic infections. Consider lower endoscopy. | If improves: Continue corticosteroids until Grade 1, then taper over \geq 1 month. If persists > 3 to 5 days or recurs after improvement: Add infliximab 5 mg/kg (if no contraindication). Note: Infliximab should not be used in cases of perforation or sepsis. |

ADL activities of daily living; CTCAE Common Terminology Criteria for Adverse Events; irAE immune related adverse event; IV intravenous.

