5.5.5. Criteria to Resume Treatment

Subjects may resume treatment with GS-1423 when drug-related AE(s) resolve(s) to Grade 1 or baseline value, with the following exceptions:

- Subjects may resume treatment in the presence of Grade 2 fatigue.

- Subjects with combined Grade 2 AST/ALT **and** total bilirubin values lasting > 7 days meeting discontinuation parameters (Section 5.5.6) should have treatment permanently discontinued.
- Drug-related Grade 2 pulmonary toxicity or colitis must have resolved to baseline before treatment is resumed.
- Drug-related endocrinopathies adequately controlled with only physiologic hormone replacement may resume treatment. (Exception: Study treatment does not need to be delayed/interrupted for subjects who experience immune-related hypothyroidism [Grades 1-2].)
- Subjects who received systemic corticosteroids for management of any drug-related toxicity must be off corticosteroids or have tapered down to an equivalent dose of prednisone \leq 10 mg/day.

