| Laboratory | 
Thrombocytopenia
 
• Grade 3 thrombocytopenia lasting > 7 days or associated with clinically significant bleeding (i.e. requires hospitalization, transfusion of blood products, or other urgent medical intervention)• Grade 4 thrombocytopenia 
Neutropenia
 
• Grade 4 neutropenia lasting > 7 days 
Electrolyte Abnormalities
 
• Grade 4 electrolyte abnormalities with clinical sequelae• Grade 4 electrolyte abnormalities unable to be corrected with supplementation/appropriate management within 72 hours of onset 
Liver Function Abnormalities (see Table 5-6)
 
• AST or ALT > 5 × ULN• Total bilirubin > 3 × ULN• Concurrent AST or ALT > 3 × ULN AND total bilirubin > 2 × ULN lasting > 7 days |
| Other | 
• Grade 2 or 3 adverse event (laboratory or non-laboratory) that does not resolve in ≤ 12 weeks• Recurrence of Grade 3 or higher adverse event (laboratory or non-laboratory)• Grade 4 non-hematologic adverse event |

* AE must be study drug related for discontinuation reasons to apply

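### The irAE management tables and the general stop and resume rules give different answers on GS-1423 for the same renal, gastrointestinal or skin event

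*Protocol*

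**What the plan says.** **Renal.** Protocol Table 5-8 (Section 5.5.4.6) delays GS-1423 for a Grade 2-3 creatinine rise and gives methylprednisolone 0.5-1.0 mg/kg/day. On return to Grade 1, steroids are tapered over at least a month and the instruction is to "resume GS-1423 therapy and routine creatinine monitoring per protocol". The next line reads "If elevations persist > 7 days or worsen: Treat as Grade 4". The Grade 4 row says "Discontinue GS-1423 therapy per protocol. Monitor creatinine daily" and has no resume step.

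**Gastrointestinal.** Table 5-4 says of Grade 2 events: "If worsens or persists > 3 to 5 days with oral corticosteroids: Treat as Grade 3-4". The Grade 3-4 row discontinues GS-1423. Otherwise Table 5-4 resumes at Grade 1.

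**Skin.** Table 5-3 allows delay or discontinuation for Grade 3-4 rash, and resumption once it improves to Grade 1.

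**General rules.** Section 5.5.4 describes the tables' status: "Management algorithms have been developed to assist investigators in assessing and managing the following groups of irAEs". Table 5-10 in Section 5.5.6 is a list of mandatory stops. It has no renal row, and its catch-all entry is a "Grade 2 or 3 adverse event (laboratory or non-laboratory) that does not resolve in" 12 weeks or less. Section 5.5.5 says "Subjects may resume treatment with GS-1423 when drug-related AE(s) resolve(s) to Grade 1 or baseline value", followed by exceptions, none of which concerns creatinine. Section 6.10.1 requires discontinuation after more than 4 weeks without dosing on QW or Q2W, whereas Section 5.5.6.1 asks only for documented consultation at that point.

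**DLT definition.** Section 3.2.3.3 counts as a DLT the "Inability to receive the first 2 doses of GS-1423 because of related toxicity", subject to the listed exclusions, and separately a toxicity-related delay of more than 2 weeks.

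**The concern.** An investigator managing a Grade 2-3 creatinine rise on its eighth day finds one page that ends GS-1423 and others that allow it to continue once the event settles. Similar conflicts exist for Grade 2 gastrointestinal events and for Grade 3 or higher skin events. No passage says which rule takes precedence.

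Two outputs are exposed. The first is the count of subjects who stop GS-1423 because of an adverse event, which SAP Section 7.1.6.1 tabulates. The second, in a narrower set of cases, is DLT status. DLT occurrence is the Part A primary endpoint (protocol Section 8.1.2) and drives the 3+3 decisions.

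**Working it through.** The plan states no figure that depends on this point, so there is none to reproduce. The check sets the rules side by side and then runs a Q2W calendar.

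**1. The rules**

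| Event | irAE table | General rules |
|---|---|---|
| Grade 2-3 creatinine rise, more than 7 days | Table 5-8: managed as Grade 4; stop, no resume step | Table 5-10: no renal row; stop if unresolved at 12 weeks. Section 5.5.5: resume at Grade 1 or baseline. Section 6.10.1: stop after more than 4 weeks without dosing. Section 5.5.6.1: consult |
| Grade 2 diarrhea or colitis persisting more than 3 to 5 days on steroids | Table 5-4: managed as Grade 3-4; stop | Table 5-10, gastrointestinal row: Grade 3 or higher only |
| Grade 2 colitis that improves | Table 5-4: resume at Grade 1 | Section 5.5.5: must return to baseline |
| Grade 3-4 rash that improves to Grade 1 | Table 5-3: resume | Section 5.5.2 and Table 5-10: discontinue for drug-related Grade 3 or higher skin events |

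**2. Distance between the renal limits**

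- On paper: 12 weeks = 84 days, and 84 − 7 = 77 days.
- On Q2W, the 4-week dosing-gap rule usually binds first for an event that holds dosing. Counting the gap from the last dose, the largest span is 28 − 7 = 21 days, when the event begins just after a dose. Later onset shortens it.

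**3. Cycle 1 calendar**

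Dose 1 is on Day 1, dose 2 is due on Day 15, and the DLT window is 28 days. With onset on Day d, more than 7 days have elapsed from Day d + 8. Onset on Day 2 gives Day 10, Day 7 gives Day 15, and Day 8 gives Day 16. The Table 5-8 stop therefore arrives by the planned dose 2 for onsets through Day 7. For later onsets it precedes dose 2 only if that dose has already been held.

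Take a related Grade 2 rise that starts on Day 2:

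- Table 5-8: stopped from Day 10, dose 2 not received, so a DLT.
- Section 5.5.5 and Table 5-10: if the event is back at Grade 1 by Day 15 with prednisone equivalent at or below 10 mg/day, dose 2 is given. There is then neither a stop nor a DLT.

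**4. The steroid condition**

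Section 5.5.5 bars resumption until steroids are stopped or are at or below 10 mg/day prednisone equivalent. Assumptions not in the documents: weight 50-90 kg, 1 mg methylprednisolone = 1.25 mg prednisone, and a linear 30-day taper to zero that starts at Grade 1 on Day 10.

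- Starting dose P = weight × mg/kg × 1.25; days to reach 10 mg: t = 30 × (1 − 10/P).
- 50 kg at 0.5 mg/kg: P = 31.25 mg, t = 20.4 days.
- 90 kg at 1.0 mg/kg: P = 112.5 mg, t = 27.3 days.
- Dose 2 falls on Day 10 + t = Day 30.4 to 37.3.
- Delay = 30.4 − 15 to 37.3 − 15 = 15.4 to 22.3 days, beyond the 14-day limit. This is a DLT on either reading.
- Time since dose 1 = 29.4 to 36.3 days, beyond 28. Section 6.10.1 therefore also stops the subject, while Section 5.5.6.1 would only require consultation.

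The readings separate only if no such course is given, or if 10 mg is reached by Day 29, that is, within 29 − 10 = 19 days of Grade 1. A front-loaded taper could do this.

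**5. Effect of one changed DLT**

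Under Section 3.2.3.1, 0 of 3 leads to escalation and 1 of 3 expands the cohort to 6. A move from 1 of 6 to 2 of 6 means that the MTD is exceeded, but this presupposes another DLT in that cohort.

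**The case against.** The best defense is that Table 5-10 is a minimum list and the irAE tables are guidance, so a stricter organ-specific rule may sit above it. Investigators may also stop treatment for any adverse event they judge a substantial risk. This is a possible reading for the renal and gastrointestinal stops, but three things weaken it. Where a duration-based stop was meant to be mandatory, it was carried across: the 2-week pneumonitis rule appears in Table 5-10 with a reference to Table 5-5, and the combined liver rule of more than 7 days appears in both Table 5-10 and Section 5.5.5. The renal rule appears in neither. The skin conflict also runs the other way, because Table 5-3 is more lenient than the mandatory list. Finally, the tables' repeated deferral to the protocol could settle the skin case but not the renal one, since the discontinuation section has no renal entry to defer to.

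Other parts of the defense stand:

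- A reader might infer that managing an event as Grade 4 makes it a Grade 4 DLT. The instruction governs management and does not regrade the event. A DLT arises only through another rule: a missed dose, a delay of more than 2 weeks, or the Grade 3 criteria.
- If onset follows dose 2, a Table 5-8 stop does not meet the missed-dose rule.
- A reader might set 7 days against 84 and call the limits twelvefold apart. Section 6.10.1 makes that comparison misleading on Q2W.

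**Conclusion.** The inconsistency is real and covers three irAE tables. For the same event, a subject may be permanently stopped or allowed to resume depending on the page followed. For the renal rule on Q2W, the disputed span is at most about 21 days. It narrows or closes when the Table 5-8 steroid course is given with a slow taper and Section 6.10.1 is applied. The mismatch between Sections 6.10.1 and 5.5.6.1 is part of the same problem.

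A reader might conclude that the primary endpoint in general depends on which page is used. The documents do not support that. DLT status differs only for a related Cycle 1 event before dose 2 that resolves in time with prednisone equivalent at or below 10 mg/day. With a month-long linear taper, both readings give a DLT. This rests on the weight, conversion and taper assumptions above and on counting the dosing gap from the last dose. Nor can a reader infer which limit was intended, because the text states no precedence.

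**What to change.** Reconcile Tables 5-3, 5-4 and 5-8 with Table 5-10 and with Sections 5.5.2, 5.5.5, 5.5.6.1 and 6.10.1. State which passage governs when they differ. State whether the instructions to manage an event as Grade 4, or as Grade 3-4, cover the GS-1423 stop or only the treatment of the event. Which limits apply is the sponsor's clinical decision.

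The SAP introduction says that the study ended after Part A. The study report should therefore also state which rule was applied to any affected subject, and DLT coding should be checked for Cycle 1 events of this kind.

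The cost is a few lines of wording, plus a check of any affected subjects. Sample size and analysis methods do not change.

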5.5.4.7. Neurological irAEs

Rule out non-inflammatory causes. If a non-inflammatory cause is identified, treat accordingly and continue therapy per protocol.

Table 5-9. Neurological irAE Management Algorithm

| Neurological irAEs | | |
|--|---|--|
| CTCAE Grade of Neurological Toxicity | Management | Follow-up |
| Grade 1 Asymptomatic or mild symptoms; intervention not indicated. | Continue GS-1423 therapy per protocol | Continue to monitor subject. If worsens: Treat as Grade 2 or Grade 3-4. |
| Grade 2 Moderate symptoms; limiting instrumental ADL. | Delay GS-1423 therapy per protocol. Treat symptoms per local guidelines. Consider 0.5-1.0 mg/kg/day methylprednisolone IV or oral equivalent. | If returns to baseline: Resume GS-1423 therapy per protocol. If worsens: Treat as Grade 3-4. |
| Grade 3-4 Severe symptoms; limiting self-care ADL; life-threatening. | Discontinue GS-1423 therapy per protocol. Obtain neurology consult. Treat symptoms per local guidelines. 1.0-2.0 mg/kg/day methylprednisolone IV or oral equivalent. Add prophylactic antibiotics for opportunistic infections. | If improves to Grade 2: Taper corticosteroids over \geq 1 month. If worsens or atypical presentation: Consider IV immunoglobulin or other immunosuppressive therapies per local guidelines. |

ADL activities of daily living; CTCAE Common Terminology Criteria for Adverse Events; irAE immune related adverse event; IV intravenous.

